## Sample size calculation

#### Sample size calculation

To determine an effect size of 0.50 with 80% power, a sample size of 72 with a type 1 error of 5% using a two-sided test would be sufficient. Assuming a 15% drop out rate, 82 patients will be enrolled. The sample size calculation is based on the assumed effect size of the primary outcome measure, the Autism Treatment Evaluation Checklist (ATEC), which is a ASD composite function score). The minimally clinically important difference based on the primary outcome measure with this instrument was 15 points. Given previous probiotic efficacy data, the effect size of 15 points is a reasonable assumption. Previous studies have shown that assuming ATEC data to be normally distributed is reasonable. Assuming a dropout rate of 10%, our sample size is reduced from 82 to 74. With a type 1 error rate of 5%, and required power of 80%, a non-parametric matched pairs analysis (Wilcoxon Signed-Rank Test) with an assumed low correlation between the subjects in the two conditions (rho=0.2), G\*Power 3.1.7 calculated that the study would achieve and 80% with a Cohen's dz effect size of 0.34. This equates to a small to medium Cohen's standard effect size of 0.37, as adjusted using the correction given in Myers, Well, & Lorch (2010) on page 147 equation 6.28.

[Myers, J.,, Well, A., and Lorch, R., 2010. *Research design and statistical analysis*. [online] Available at: <https://books.google.co.uk/books?hl=en&lr=&id=nbsOIJ\_saUAC&oi=fnd&pg=PR2&dq=Research+Design+and+Statistical+Analysis:+Third+Edition&ots=ZwDnkDkrpH&sig=IVDU30D2I5sa5MMmvqAOw5FstZc> [Accessed 10 May 2017].]

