The efficacy of the multi-strain probiotic, Vivomixx, on behaviour and gastrointestinal symptoms in children with autism spectrum disorder (ASD)

NCT03369431

18th March 2021

Statistical Analysis Plan

Principal Analysis

The principal analysis will look for between phase differences in outcome measures assuming no order of treatment effects, which will be investigated in the secondary analysis. The outcome variables consider are:

1. Change from baseline ATEC scores (**Interval Data: between groups**): **PRIMARY OUTCOME MEASURE**

Secondary measures

1. Change from baseline ABC scores (**Interval Data: between groups**)
2. Gastrointestinal events: frequency of abdominal pain, gaseousness, diarrhoea, constipation, pain on stooling, and difficulty swallowing. (**Interval Data: between groups**)
3. Bristol Stool Scale: proportion of phase participants with type 4 stool samples after active treatment. (**Dichotomous data: between groups**)
4. Clinical Global Impression (**Interval Data: between groups**)
5. Treatment Effectiveness Score (**Interval Data: between groups**)
6. Correlations: ATEC vs constipation frequency on GI History; ATEC vs diarrhoea frequency on GI History; ATEC vs ATEC components (i.e. Health/Physical/Behaviour scores); ATEC vs Clinical Global Impression. (**Interval Data: Correlation**)

All between groups interval data will be subject to the following protocol for statistical analysis.

1. Calculation of mean, standard error and median and 25-75 quartiles for both phases.
2. Kolmogorov-Smirnov test to assess normality in the between phase differences in primary and secondary outcome measure with interval measurements.
3. If there is no statistically significant ($\alpha = 0.05$) evidence of non-normality in the mean differences then a paired t-test¹ will be used to assess statistical significance.
4. If there is statistically significant ($\alpha = 0.05$) evidence of non-normality in the mean differences, then a Wilcoxon-Signed-rank-test will be used to assess statistical significance.

All between groups dichotomous data will be assessed for statistical significance by calculating the Relative Risk and corresponding 95% confidence intervals for exposure to the active agent. Corresponding p-values can, if desired, be calculated from the 95% Confidence Intervals; however, 95% Confidence Intervals that do not contain the value 1 are statistically significant at $\alpha = 0.05$.

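### The detectable effect of 0.37 does not follow from dz = 0.34 at rho = 0.2 (which gives about 0.43), and 82 enrolled does not give 72 completers at 15% dropout

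*Protocol*

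**What the plan says.** Everything is in the Protocol, section Sample size calculation, which contains two calculations.

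- **First calculation.** For an effect size of 0.50 at 80% power, "a sample size of 72 with a type 1 error of 5% using a two-sided test would be sufficient". It continues: "Assuming a 15% drop out rate, 82 patients will be enrolled". It names no test and no correlation.
- **Clinical target.** "The minimally clinically important difference based on the primary outcome measure with this instrument was 15 points". No ATEC standard deviation is given.
- **Second calculation.** "Assuming a dropout rate of 10%, our sample size is reduced from 82 to 74". With 5% type 1 error, 80% power, a Wilcoxon signed-rank test and a "low correlation between the subjects in the two conditions (rho=0.2"), the detectable dz is given as 0.34. This is then equated to a "standard effect size of 0.37, as adjusted using the correction given in" a cited textbook equation, which the documents do not reproduce.

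The Protocol Summary repeats the total of 82. The SAP (Principal Analysis) also plans a paired comparison: a paired t-test by default and, if the differences depart significantly from normality, "then a Wilcoxon-Signed-rank-test will be used to assess statistical significance".

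**The concern.** The paragraph supplies every input needed to check its last step, and that step does not agree with them. The value 0.37 is the only statement, on the d scale, of the smallest effect the trial can detect. If it is too small, the plan overstates its sensitivity, and a null result read against it would seem to rule out smaller effects than the trial could reliably detect.

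The enrolment figure has a similar fault. A total of 82 does not deliver the 72 completers called sufficient at the dropout rate given beside it, and a second, lower dropout rate is then applied to the same 82. The reader cannot tell how many completers the plan rests on.

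**Working it through.** **Inputs (Protocol, Sample size calculation):** two-sided 5% (the sidedness is stated in the first calculation only); 80% power; 72 and 74 completers; 82 enrolled; dropout 15% and 10%; rho = 0.2; dz = 0.34; d = 0.37; target 0.50; 15 ATEC points.

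**Method.** Power comes from the noncentral t distribution for paired data. For the Wilcoxon test, n is multiplied by 3/π, its relative efficiency for normal data. Simulated signed-rank tests agreed.

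**1. What reproduces**
- 82 × 0.90 = 73.8, so 74 completers.
- n = 74 with dz = 0.34 gives power 0.805 by two-sided Wilcoxon (0.823 by paired t). The stated dz is right, and this confirms the two-sided reading.

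**2. Conversion from dz to d**
- With equal SDs in the two conditions, SD of the difference = SD × √(2(1 − rho)), so d = dz × √(2(1 − rho)).
- At rho = 0.2: d = 0.34 × √1.6 = 0.430. Rounding of dz (0.335 to 0.345) gives 0.424 to 0.436.
- The rho that would give 0.37 is 1 − (0.37/0.34)²/2 = 0.408. With both figures rounded, it lies between 1 − (0.375/0.335)²/2 = 0.373 and 1 − (0.365/0.345)²/2 = 0.440. At rho = 0.4, d = 0.34 × √1.2 = 0.372.

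**3. Power for d = 0.37 at rho = 0.2**

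Here dz = 0.37/√1.6 = 0.2925.

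| Completers | Wilcoxon | Paired t |
|---|---|---|
| 74 | 0.68 | 0.70 |
| 69–70 | 0.65 | 0.67–0.68 |

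Reaching 80% would take 99 pairs by Wilcoxon or 94 by paired t. The effect detectable at 80% power is d = 0.43 with 74 completers and 0.44 with 69–70 (0.42 and 0.43 by paired t).

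**4. Dropout**
- 72/0.85 = 84.7, so 85 must be enrolled.
- 82 × 0.85 = 69.7 completers.
- 72 completers out of 82 means a dropout of 1 − 72/82 = 12.2%.
- 72 × 1.15 = 82.8. Multiplying by 1.15 instead of dividing by 0.85 may be where 82 came from.

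**5. The 0.50 target**
- Read as d at rho = 0.2: dz = 0.50/√1.6 = 0.395. Wilcoxon power is 0.89 at 69–70 completers, 0.90 at 72 and 0.91 at 74. At rho = 0 it is still 0.82 at 72.
- So 72 is sufficient but not the minimum. At rho = 0.2, 55 pairs reach 80% (53 by paired t).

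**6. The 15-point difference**

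No SD is given. If 15 points and 0.50 are the same target, the implied SD is 15/0.50 = 30, but the Protocol does not say so. The SDs below are assumptions (Wilcoxon, rho = 0.2).

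| Assumed SD | d = 15/SD | Power, n = 74 | Power, n = 70 |
|---|---|---|---|
| 30 | 0.50 | 0.91 | 0.89 |
| 35 | 0.43 | 0.80 | 0.78 |
| 40 | 0.375 | 0.69 | 0.67 |

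**The case against.** **The cited equation cannot be seen.** The Protocol attributes 0.37 to a textbook correction that is not reproduced, so the slip could lie in the formula, the definition of the effect size, or rho. If the conversion used rho = 0.4, then 0.37 has 80% power at 74 completers and the stated rho is what needs correcting. This stands as a limit: the 68% holds only if rho = 0.2 is the intended correlation. It does not rescue the paragraph, which gives one rho and an effect size that does not fit it.

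**The SAP's default is the paired t-test.** For that test the figures are slightly kinder: power 0.70 for 0.37, and a detectable effect of 0.42 at 74 completers. The Protocol's own calculation names Wilcoxon, and the conclusion is the same under either test.

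**Nothing turns on it.** No decision rule uses 0.37, enrolment falls short by three, and the 0.50 target is well powered. This stands as to consequence. The figures are still wrong as written.

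**The SD scenarios are hypothetical.** They are. They show only that power for 15 points cannot be judged without an SD, and this missing detail is secondary to the two figures that fail to reproduce.

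**Conclusion.** The concern holds. At the stated rho = 0.2, dz = 0.34 corresponds to d of about 0.43, not 0.37. If rho = 0.2 is intended, an effect of 0.37 has about 68% power at 74 completers (70% by paired t), not 80%. An enrolment of 82 with 15% dropout yields about 70 completers, not 72; 85 would be needed. Two dropout rates are applied to the same 82.

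This rests on the standard dz-to-d relation with equal SDs in the two conditions, approximately normal differences, and a two-sided 5% paired test. It is a reporting error that overstates sensitivity, not evidence that the trial is underpowered for its 0.50 target. Whether 15 points has 80% power depends on an SD that the documents do not give; the threshold is about 35 at 74 completers and 34 at 70. The paragraph should be corrected, and confidence in the arithmetic is high.

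**What to change.** Reword the section and leave enrolment at 82.

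- Choose one dropout rate. With 10%: 74 completers and 80% power for dz = 0.34, which is d of about 0.43 at rho = 0.2. With 15%: 69–70 completers, dz of about 0.35 and d of about 0.44.
- If a rho other than 0.2 was used for the conversion, state it and use it throughout.
- Keep the 0.50 target, but name its test and rho and report its actual power (about 0.89–0.91 at rho = 0.2 with 69–74 completers).
- State the ATEC SD that ties 15 points to the standardised effect, with its source.

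The cost is wording only: enrolment, test and endpoint do not change. The stated detectable effect becomes less favourable (0.43–0.44 instead of 0.37), and stating the SD may show that 15 points has less than 80% power if the SD is above about 35.

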## **Planned Recruitment Rate**

The maximum possible recruitment rate will be 15 participants per week. The expected recruitment rate is estimated as 4 participants per week. Given the number of participants seen by the two charities, we would expect approximately 50 patients per week to be self-referred.

### **Randomisation methods**

The participants will be randomised in blocks that are multiples of 4 so that in each block of 4 there will be 2 participants in group A and 2 participants in group B (ie "2x2"). There will be no stratification. There will be equal allocation between the treatment arms.

The randomisation list is drawn by a specific software and prepared by a contract research organisation (CRO). Participant numbers will be allocated sequentially to the recruited participants on the basis of their order of recruitment to the study.

## **Statistical analysis**

#### Summary of baseline data and flow of participants

As the study is a crossover study, each participant becomes their own control so there is not a need to compare characteristics between the two study arms. Baseline variables as follows will be collected and used in statistical analyses to see whether they are associated with treatment response:

Age ATEC score (done by parent) ATEC score (done by educator) ABC total score and subscale scores GIH frequency score Clinician's global assessment

We plan to produce a CONSORT flow diagram.

#### **Stool Microbiome Analysis**

After collection and prior to processing, the samples will be anonymised by means of a bar-coding system. This will ensure that any laboratory staff handling the samples will not be able to identify the donor. The samples will be analysed using a non-culture technique involving 16s rRNA gene amplification and analysis. The prepared samples will be analysed using the Illumina high-throughput sequencing platform. The 16s rRNA gene is ubiquitous to bacteria, but is not found in humans. The use of targeted DNA amplification ensures that only bacterial DNA can be sequenced. The results will then be analysed using bioinformatics and standard statistical software.

#### Primary outcome analysis

The intention-to-treat (ITT) analysis will be performed on all participants who are randomised. An additional analysis will be done on only those participants who complete the study per protocol analysis.

Change in the ATEC score during follow-up will be examined using the mixed model for analysis of variance to account for missing data (dropouts). This model allows the evaluation of the effect of each factor on the outcome as well as the interactions between factors. The mixed model will use group (treatment ASD - vivomixx protocol v6.docx, IRAS 204582, Version 6.0, 30/01/2020, Page 43 of 57

versus control) and time as factors. If residuals prove not to be normally distributed, the Bonferroni multiple comparisons with Bootstrap multiple comparisons to accommodate for the non-normality of residuals will be done. A P-value <0.05 is considered significant and multiple comparisons will be undertaken with Fisher's least significant difference test and 95% confidence intervals.

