## **Statistical Considerations**

### **Primary Outcome**

Our primary outcome is a change in the baseline Autism Treatment Evaluation Checklist (ATEC) total score to the total score after 12 weeks and 28 weeks of treatment.

The ATEC was developed in 1999 by Bernard Rimland and Stephen M. Edelson of the Autism Research Institute, as a measure to evaluate treatment effectiveness in the ASD population. It was developed to address the need for an easy to administer, sensitive to change and valid instrument specifically developed for children with ASD.

The ATEC is a one-page form, designed to be completed by parents, teachers, or caregivers. It consists of 4 subtests: I. Speech/Language Communication (14 items); II. Sociability (20 items); III. Sensory/

ASD - vivomixx protocol v6 .docx, IRAS 204582, Version 6.0, 30/01/2020, Page 40 of 57

Cognitive Awareness (18 items); and IV. Health/Physical/Behavior (25 items). The scale covers 77 items and gives a total score and scores for each of the 4 sub-sections. The higher the score, the greater the disability overall or in a sub-section. The ATEC total score can range from 0 - 180 and is calculated by summing the scores of each subsection. Geier et al [60] compared the ATEC to the Childhood Autism Rating Scale (CARS) and found significant correlation between total ATEC and CARS scores. Many studies have successfully used the ATEC to measure treatment effects in autism or to measure the severity of autism [61][62][63][64][65][20][66][67][68].

Other instruments such as the Autism Diagnostic Interview-Revised (ADI-R), the Autism Diagnostic Observation Schedule (ADOS) and the Childhood Autism Rating Scale (CARS) have been used to assess progress or response to treatment, but these were primarily developed as diagnostic instruments and as such are designed to show overall *stability* over time and not to be sensitive to change. These measures also do not assess the physical and systemic issues in ASD. The ATEC is unique in that it does address these issues. It has recently been validated against the CARS, which is an established, professional-related measure of autism [60].

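### The Protocol ties Bonferroni to non-normal residuals, sets unreconciled Fisher LSD beside it and names no single primary contrast; the SAP tests one contrast but does not withdraw that rule

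*Protocol*

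**What the plan says.** Protocol, Primary Outcome, defines the outcome as "a change in the baseline Autism Treatment Evaluation Checklist (ATEC) total score to the total score after 12 weeks and 28 weeks of treatment". Neither time point is made decisive, and no active-minus-placebo contrast is written down.

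Protocol, Primary outcome analysis (repeated in the Protocol Summary), fits a mixed model with group and time, chosen to cope with dropouts. It then gives two rules in succession. The first is "If residuals prove not to be normally distributed, the Bonferroni multiple comparisons with Bootstrap multiple comparisons to accommodate for the non-normality of residuals". The second sets significance at P<0.05 and says that "multiple comparisons will be undertaken with Fisher's least significant difference test and 95% confidence intervals". The second carries no condition. Nothing says whether an overall test must come first or which comparisons are meant.

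Protocol, Sample size calculation, works with "a type 1 error of 5% using a two-sided test" and in its paired calculation reaches "80% with a Cohen's dz effect size of 0.34", for one matched-pairs test.

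Protocol, Sensitivity and other planned analyses, defers to a more detailed SAP. That SAP (18 March 2021), under Principal Analysis, tests change in ATEC once, between phases, assuming no order effect. It uses a paired t-test, or a Wilcoxon signed-rank test if a Kolmogorov-Smirnov test rejects normality. Order effects are examined only in its secondary analysis. It does not mention the mixed model, Bonferroni or LSD.

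**The concern.** Residual shape and number of comparisons are separate problems. A bootstrap can deal with the first; Bonferroni deals only with the second. Attaching Bonferroni to a normality finding means that multiplicity control could depend on something that has no bearing on it. With LSD named next to it, the text holds two different multiplicity rules and no way to choose between them.

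The primary false-positive rate is at stake, and so is what is being estimated. A model with group and time, followed by pairwise comparisons, leads naturally to group comparisons at week 12 and at week 28. These visits fall at the ends of the two crossover periods. If group means randomised sequence, the week-12 comparison uses only the first period, and by week 28 each group has been assigned both products. Neither comparison is the within-child active-minus-placebo effect for which the design was chosen.

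**Working it through.** **Inputs.** From Protocol, Sample size calculation: two-sided 5%, 80% power, dz = 0.34, 82 enrolled and 10% dropout. From Protocol, Primary Outcome: two time points. The correlation between the two test statistics is not given and is assumed here. The rho of 0.2 in the sample size section is between conditions and is a different quantity.

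**1. The plan's own figure.** 82 × 0.9 = 73.8, so 74 children.
- Paired t-test: noncentrality 0.34 × √74 = 2.925; power 82.3%.
- Wilcoxon (efficiency 3/π): effective n = 74 × 3/π = 70.7; noncentrality 0.34 × √70.7 = 2.86; power 80.5%.

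The stated 80% is reproduced. It belongs to one paired contrast at 5%.

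**2. Two ungated 5% tests, either counting as success.** If independent, the error is 1 − 0.95² = 9.75%. If correlated, it is 1 − P(|Z1| < 1.96 and |Z2| < 1.96):

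| Assumed correlation | Family-wise error |
|---|---|
| 0 | 9.75% |
| 0.2 | 9.6% |
| 0.5 | 9.1% |
| 0.7 | 8.3% |
| 0.8 | 7.8% |
| 0.9 | 7.0% |

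It exceeds 8% only when the correlation is below about 0.77.

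**3. LSD applied only after an overall test.** With no treatment effect:
- Joint 5% test of the two comparisons: 4.7%, 4.6%, 4.1% and 3.5% at correlations 0, 0.2, 0.5 and 0.8.
- Gate on the group-by-time interaction (simulation, 37 per arm, three visits): about 4%.
- Gate on the time effect alone, same simulation, visit correlations 0.2 to 0.7: below 1% with no trend, about 5% to 9% with a shared improvement of 0.3 SD, and about 9% with 0.5 SD. The trends are assumed values.

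So whether LSD protects depends on the gate, which the Protocol leaves open.

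**4. The SAP's single test.** Simulated at n = 74, the t-or-Wilcoxon procedure has size 4.6% to 5.0% for normal, t3 and lognormal-difference data.

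**5. Keeping two comparisons with Bonferroni.** At 0.025 each, the error is 1 − 0.975² = 4.9% if independent. Wilcoxon power per comparison falls from 80.5% to 71.4%.

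**6. The missing period term.** Assume that a period effect shifts the paired difference by +0.5 SD in one sequence and −0.5 SD in the other. The pooled SD rises from 1 to √(1 + 0.25) = 1.118, and the critical value becomes 1.993 × 1.118 = 2.228 on the true standard-error scale.
- Error: 2 × (1 − Φ(2.228)) = 2.6%, against the nominal 5%.
- Power: Φ(2.925 − 2.228) = 76%, against Φ(2.925 − 1.993) = 82% with no period effect.

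In simulation, the period-adjusted test keeps about 5% and 82%.

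**The case against.** The strongest reply is that the SAP governs. The Protocol itself delegates to a later plan, and that plan has one primary test, no LSD, no Bonferroni and no pair of time-point tests.

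A reader might nonetheless infer that the stated 5% error becomes 8% to 10%, or that LSD is what happens whenever residuals are normal. The documents do not support either reading:

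- The LSD sentence is unconditional. Reading it as the alternative to Bonferroni is an inference.
- Fisher's LSD in its usual form follows a significant overall test. The Protocol neither requires nor excludes one.
- No either-counts success rule is stated. If both time points had to succeed, the error could not exceed 5%.
- The Protocol glosses group as treatment versus control. If it is coded by the product taken in each period, its main effect is a single contrast.
- No correlation between the tests is given, and above about 0.77 even the ungated figure falls below 8%.

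All of this stands and removes any claim that the trial's primary error is inflated. It does not remove the textual defect. Bonferroni is still attached to the wrong problem in the current Protocol, and the text does not say how group is coded for a child who changes product. The SAP replaces the mixed model without saying so. Without imputation, its paired test uses only children with values in both periods, whereas the Protocol promises an analysis of all randomised participants by a model suited to dropouts. Anyone who restores that model for this reason restores its comparison rule too.

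**Conclusion.** The concern holds as an invalid and ambiguous multiplicity rule in the Protocol, together with a primary analysis that the two documents state differently. The possible inflation is to about 7% to 10% against 5%. It rests on three assumptions that the documents do not make: separate group comparisons at weeks 12 and 28, no effective overall test, and success on either. The range covers assumed correlations from 0.9 down to 0. Under the SAP's single paired test the inflation does not arise. What remains there is the absence of a period term, which under the assumed period effect makes the test conservative and costs about six points of power. This should be corrected, but it does not show that the SAP's primary test exceeds its nominal level.

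**What to change.** - In the Protocol Summary and in Primary outcome analysis, delete the Bonferroni and LSD sentences.
- In Protocol and SAP alike, state one primary contrast: active minus placebo ATEC over the two treatment periods, from a mixed model with child as a random effect and period and treatment as fixed effects, tested at two-sided 5%.
- If residuals are non-normal, give a bootstrap confidence interval for that same contrast.
- Report the week-12 and week-28 group means descriptively, without tests.
- Say in the SAP that this analysis replaces the Protocol's group-and-time model.

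The cost is wording in two documents and one degree of freedom for period. No further data or participants are needed, and with one pre-named contrast no multiplicity correction is required, so the power loss in step 5 is avoided.
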